3.1.3. Primary Safety Endpoints

In general, e-diary data that are confirmed as errors will not be used for derivation or analysis.

Feedback was received from the FDA on reactogenicity data collection and analysis. Most recently, the FDA stated the concern of missing e-diary entries for reactogenicity events. However, Pfizer sends reminders to sites to follow up on missing e-diary entries, and the reminders are also sent to sites from the vendor. Also, CRF completion guidelines do allow sites to enter e-diary events into the AE CRF. Therefore, Pfizer uses both sources for the reactogenicity data: the e-diary and the AE CRF. Since the AE CRF did not designate a specific page to collect reactogenicity data that were missing in the e-diary, Pfizer has adopted a process of providing a listing of AEs reported within 7 days after vaccination to the clinical team to review/query the AEs, and to finalize the PTs that should be considered reactogenicity before the database lock. For the AEs reported on the same day of vaccination but missing the AE start time, these AEs are defaulted to be considered AEs after vaccination. Then any AEs reported within 7 days after vaccination that match with those flagged PTs, (either "related," or unrelated as assessed by the investigator) will be pooled with reactogenicity data from the e-diary. If the same reactogenicity is reported on the same day from both the e-diary and the AE CRF, the highest grade from the 2 data sources will be used for that specific day.

> DMB02-GSOP-RF02 7.0 Statistical Analysis Plan Template 31-Jan-2022 PFIZER CONFIDENTIAL TMF Doc ID: 98.03 Page 17 of 46

It should be noted that the data collection in the AE CRF is different from that of the e-diary:

- For redness, swelling, and fever, the measured size of redness and swelling at the injection site and temperature are recorded in the e-diary, but not in the AE CRF. Therefore, the maximum grading for the 3 items reported in the e-diary will be based on actual size and the FDA toxicity grading scale, but the maximum grading of the 3 reactogenicity terms from the AE CRF will be based on the grading scale on the CRF page. For the 7 days, only the maximum grading from both sources will be used for the aggregated severity analysis, though the grading algorithm is different between the 2 data sources.

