- For pain at the injection site and all other systemic events, the severity grading algorithm for the e-diary data and the AE CRF may not be the same, though Pfizer will choose the highest-severity grade.

If a participant did not have any e-diary data transferred, the AE CRF data will not be used for derivation because the analysis of reactogenicity will be based on e-diary safety population, which is only restricted to participants who have at least 1 day of e-diary data entered. In other words, if a participant did not report any e-diary data, the participant will not be included in the analysis of reactogenicity data.

Safety	Vaccine Group (as Received)				
Endpoints	Combination:	Sequential	qIRV Alone	RSVpreF	Placebo Only
	RSVpreF +	Administration:		Alone	
	qIRV	qIRV/RSVpreF			
Local	Local reactions	Local reactions	Local reactions	Local reactions	Local reactions
reactions	reported within	reported within	reported within	reported within	reported within
within	7 days after	7 days after	7 days after	7 days after	7 days after
7 days after	Vaccination 1	Vaccination 1 or	Vaccination 1	Vaccination 2	Vaccination 2
vaccination	among	after Vaccination 2	among	among	among
	participants who	among participants	participants who	participants who	participants who
	received the	who received qIRV	received qIRV at	received	received placebo
	combination	at Visit A101 with	Visit A101 with	RSVpreF at	only at Visit
	vaccine at	at least 1 day of	at least 1 day of	Visit A102 with	A102 with at
	Visit A101 with	e-diary transferred	e-diary data	at least 1 day of	least 1 day of
	at least 1 day of	following the	transferred	e-diary data	e-diary data
	e-diary data	vaccination and	following the	transferred	transferred
	transferred	received RSVpreF	vaccination.	following the	following the
	following the	at Visit A102 with		vaccination.	vaccination.
	vaccination.	at least 1 day of			
		e-diary data			
		transferred			
		following the			
		vaccination.			

The table below lists safety endpoints that will be derived for each vaccine group.

DMB02-GSOP-RF02 7.0 Statistical Analysis Plan Template 31-Jan-2022 PFIZER CONFIDENTIAL TMF Doc ID: 98.03 Page 18 of 46

Safety	Vaccine Group (as Received)				
Endpoints	Combination: RSVpreF + qIRV	Sequential Administration: qIRV/RSVpreF	qIRV Alone	RSVpreF Alone	Placebo Only

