3.1.3.3. Adverse Events

Standard algorithms for handling missing AE dates and missing AE severity will be applied as described in the Pfizer vaccine data standard rules.

For any AE reported in the CRF that was considered as reactogenicity (Section 3.1.3) during the clinical review and data-pooling process, this AE record will not be included in any of the derivations included in Section 3.1.3.3 and Section 3.1.3.4. However, if those reactogenicity AEs lead to discontinuation or were serious AEs, they will still be included in AE data.

The following derivations will be included for each participant:

- 1. Any AE reported within 1 month after vaccination: If the AE started on the same day of vaccination, and the AE start time is before the vaccination time, then this AE will not be counted. Otherwise, if the AE start time is missing or after the vaccination time, the AE will be included.
- 2. Any related AE reported within 1 month after vaccination: This is similar to the above except only the related AE is included (but excluding the related reactogenicity reported within 7 days of vaccination [Section 3.1.3]).
- 3. Any immediate AE reported after vaccination (AE start time is within 30 minutes after vaccination): Only those AEs that start on the same day of vaccination, and with nonmissing AE start time that is within 30 minutes of vaccination, will be included.
- 4. Any severe AE reported within 1 month after vaccination.

- 5. Any life-threatening AE reported within 1 month after vaccination.
- 6. Any AE leading to study withdrawal within 1 month after vaccination.
- 7. Any SAE reported within 1 month after vaccination.
- 8. Any AESI within 1 month after vaccination, based on the AE PT.

The following events are considered AESIs:

- Confirmed diagnosis of influenza.
- Confirmed diagnosis of RSV infection.
- Confirmed diagnosis of myocarditis or pericarditis within 4 weeks after Vaccination 1. See Section 3.6.3 for the evaluation of potential myocarditis or pericarditis.

Each of the above will be derived for the data presentation with 5 vaccine groups. Specifically, for the vaccine group receiving sequential administration of qIRV/RSVpreF, the endpoints will be derived after Vaccination 1 and Vaccination 2.

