3.2.1.1. Adverse Events

In Substudy B, AEs will be collected throughout the study. The following derivations will be included for each participant:

- 1. Any AE reported from vaccination throughout the study: If the AE started on the same day of vaccination and the AE start time is before the vaccination time, then this AE will not be counted. Otherwise, if the AE start time is missing or after the vaccination time, the AE will be included.
- 2. Any related AE reported from vaccination throughout the study: This is similar to the above except only the related AE is included (but excluding the related reactogenicity reported within 7 days of vaccination [Section 3.1.3]).
- 3. Any immediate AE reported after vaccination (AE start time is within 30 minutes after vaccination): Only those AEs that start on the same day of vaccination, and with nonmissing AE start time that is within 30 minutes of vaccination, will be included.
- 4. Any severe AE reported from vaccination throughout the study.
- 5. Any life-threatening AE from vaccination reported throughout the study.
- 6. Any AE leading to study withdrawal after vaccination.
- 7. Any SAE reported from vaccination throughout the study.
- 8. Any AESI from vaccination throughout the study, based on the AE PT.

The following events are considered AESIs:

- Confirmed diagnosis of influenza.
- Confirmed diagnosis of RSV infection.
- Confirmed diagnosis of myocarditis or pericarditis within 4 weeks after vaccination. See Section 3.6.3 for the evaluation of potential myocarditis or pericarditis.

Each of the above will be derived for the data presentation with 2 vaccine groups and the age groups of 50-64 years, 65+ years and 50+ years.

The same algorithm as stated in Section 3.1.3, for any AE reported in the CRF that was considered as reactogenicity during the clinical review and data-pooling process, this AE record will not be included in any of the derivations included in Section 3.1.3.3 and Section 3.1.3.4. However, if those reactogenicity AEs lead to discontinuation or were serious AEs, they will still be included in AE data.

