5.3.1.1. Reactogenicity Data

For derived variables based on reactogenicity data, if any day of the 7-day e-diary is available, the "any day (Day 1 through Day 7)" data will be considered nonmissing.

The reactogenicity data are collected through the e-diary, which does not allow participants to skip the question. Therefore, for a specific day, if the e-diary data are transferred for that day, all of the reactogenicity data for the participant on that day are nonmissing. No missing reactogenicity data will be imputed other than what is described in Section 3.1.3. In summary, for any participant with all 7 days of the e-diary missing, this will not be included in the analysis (ie, assuming MCAR).

DMB02-GSOP-RF02 7.0 Statistical Analysis Plan Template 31-Jan-2022 PFIZER CONFIDENTIAL TMF Doc ID: 98.03 Page 35 of 46 Based on data from available studies, the missing data for reactogenicity are minimal, which is consistent with Li et al.⁴ No sensitivity analysis is planned for reactogenicity data.

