6.5. Safety Summaries and Analyses

6.5.1. Adverse Events

For both SSA and SSB: For all of the AEs categorized in Section 3.1.3.3 and Section 3.1.3.4, each individual AE including SAE after vaccination will be categorized by the MedDRA PT and descriptively summarized with count, percentage, and 95% CI for vaccine group.

For Tier 1 events, the 2-sided 95% CIs for the difference in the percentage of participants reporting the events between the RSVpreF contained group and the control group will be calculated using the test statistic proposed by Miettinen and Nurminen³; in addition, the asymptotic p-values will also be presented for the difference in the percentage of participants reporting the events, based on the same test statistic and under the assumption that the test statistic is asymptotically normally distributed.

Because all participants enrolled in this study are expected to receive either RSVpreF or (RSVpreF+qIRV), there is no control in this study. Therefore, the intervention group will be all participants who received (RSVpreF+qIRV) or RSVpreF from both SSA and SSB, and the control group will be from RSVpreF pivotal Phase 3 study (C3671013) who received placebo only. The count for each Tier 1 event and denominator from C3671013 placebo group will be provided in this Tier 1 AE analysis.

It should be recognized that most studies are not designed to reliably demonstrate a causal relationship between the use of a pharmaceutical product and an AE or a group of AEs. Except for selecting events in unique situations, studies do not employ formal adjudication procedures for the purpose of event classification. As such, safety analysis is generally considered an exploratory analysis and its purpose is to generate hypotheses for further investigation.

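### Read literally, the SAP leaves non-serious, non-discontinuing reactogenicity-type CRF events out of both the reactogenicity and the AE tables when the participant has no e-diary data for that vaccination

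*SAP*

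**What the plan says.** SAP 3.1.3 draws reactogenicity from two sources, the e-diary and the AE CRF. Before database lock the clinical team reviews a listing of AEs from the first 7 days to "finalize the PTs that should be considered reactogenicity before the database lock". Then "any AEs reported within 7 days after vaccination that match with those flagged PTs", whether judged related or not, are pooled with the diary data.

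The same section limits the pooling: "If a participant did not have any e-diary data transferred, the AE CRF data will not be used for derivation". SAP 5.3.1.1 agrees: "for any participant with all 7 days of the e-diary missing, this will not be included in the analysis". The Substudy A endpoint table in 3.1.3 asks for at least one day of diary data after the specific vaccination.

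SAP 3.1.3.3 then deals with the AE side. Of a CRF event considered reactogenicity during clinical review and pooling, it says "this AE record will not be included in any of the derivations included in Section 3.1.3.3 and Section 3.1.3.4". The next sentence makes an exception: "if those reactogenicity AEs lead to discontinuation or were serious AEs, they will still be included in AE data". SAP 3.2.1.1 carries the rule and the exception to Substudy B, "for any AE reported in the CRF that was considered as reactogenicity during the clinical review and data-pooling process". In both sections, item 2 (related AEs) also excludes related reactogenicity from the first 7 days. SAP 6.5.1 builds the preferred-term tables from the same sections: "For all of the AEs categorized in Section 3.1.3.3 and Section 3.1.3.4".

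**The concern.** Taking solicited-type events out of the AE tables is sensible when the same event is already counted as reactogenicity. Protocol 8.3.4 gives avoidance of double reporting as the reason for keeping diary data off the AE CRF. For a participant without a diary there is no second record, so removal does not prevent a double count. It deletes the only count.

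Such records can be expected. Under Protocol 8.3, acute reactions in the first 30 minutes are documented on the AE CRF whether or not a diary is later completed. SAP 3.1.3 also notes that sites may enter diary-type events there. An injection-site reaction seen by staff could therefore drop out of the immediate-AE endpoint (item 3 of 3.1.3.3 and of 3.2.1.1).

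AEs are a primary safety endpoint in both substudies. Protocol Table 5 promises a summary of all AEs in the month after each vaccination, SAP 2.1 declares no departure from the protocol's analysis, and SAP 6.1.4.1 says that everything collected is included. The literal rule does not deliver that.

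**Working it through.** The plan states no figure on this point, so there is none to reproduce. The check traces one record and then bounds the number affected.

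**Trace.** Take a non-serious injection-site reaction on Day 1, entered on the AE CRF, not leading to discontinuation, in a participant with no e-diary data after that vaccination.

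| Step | SAP section | Result |
|---|---|---|
| Flagging | 3.1.3 | By preferred term and 7-day window; diary status plays no part, so the record is flagged |
| Reactogenicity tables | 3.1.3, 5.3.1.1 | CRF data not used; participant not in the analysis |
| AE derivations, Substudy A | 3.1.3.3 | Flagged record removed; neither exception applies |
| AE derivations, Substudy B | 3.2.1.1 | Same rule, but the text names 3.1.3.3 and 3.1.3.4 rather than 3.2.1.1; item 2 has its own exclusion |
| Preferred-term tables | 6.5.1 | Built from 3.1.3.3 and 3.1.3.4; record not recovered |

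If the participant had a diary, the record would be pooled and counted once. Without one it is counted zero times.

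**Upper bound.** Group sizes are 125 (Protocol 1.1.1.3) and 100 (Protocol 1.1.2.3). The non-transmission fraction f is not in the documents; 2%, 5% and 10% are assumed. Maximum participants affected = n × f, rounded down. Maximum fall in the any-AE rate = that number / n.

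| f | n = 125 | n = 100 |
|---|---|---|
| 2% | 2.5, so 2 (1.6 points) | 2 (2.0 points) |
| 5% | 6.25, so 6 (4.8 points) | 5 (5.0 points) |
| 10% | 12.5, so 12 (9.6 points) | 10 (10.0 points) |

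To reach the bound, every participant without a diary would need a flagged CRF event, no other countable AE, and neither exception.

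**AE table, illustration with assumed counts.** If 18 of 125 had a countable AE and 6 of them are lost, the rate moves from 18/125 = 14.4% (Clopper-Pearson 95% CI 8.8 to 21.8) to 12/125 = 9.6% (5.1 to 16.2). The denominator does not change.

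**Reactogenicity table, same 6 participants.** They leave numerator and denominator together, so the reported rate might be 78/119 = 65.5%. Had all 6 reacted, the full-group rate would be (78 + 6)/125 = 67.2%. Had none reacted, it would be 78/125 = 62.4%. The reported figure can lie on either side of the full-group rate.

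**The case against.** The best defence is the qualifier in 3.1.3.3, which ties the removal to clinical review and data pooling and refers back to 3.1.3. A record that 3.1.3 forbids from being pooled may not count as one considered reactogenicity in that process, and would then stay in the AE tables. The statement in 6.1.4.1 that all collected data are included favours this reading. It is tenable, but the SAP does not state it, flagging is by term alone, and item 2 in both sections excludes related reactogenicity without any condition that it was pooled. Two programmers could reasonably differ.

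For Substudy B, the removal literally points at the Substudy A derivations. That is probably a drafting slip, but it means the loss is less firmly stated there.

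Mitigations exist. Sites are reminded about missing diary entries and the clinical team queries early AEs (SAP 3.1.3). Diary completion is summarized by vaccine group (6.4.2), and SAP 5.3.1.1 describes missing reactogenicity data as minimal. These make the number small and diary non-completion visible. They do not put the events back into a table.

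A reader might also infer a breach of the treatment-policy strategy. The documents do not support that: the strategy concerns intercurrent events, and a missing diary is not among those listed in SAP 2.2.1.1 and 2.2.1.2. Limiting CRF supplementation to participants with diary data is also consistent with Protocol 9.3.1. The difficulty lies only in removing the remaining records from the AE side.

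**Conclusion.** The gap is real on the literal text, for non-serious flagged events in the first 7 days that do not lead to discontinuation, in participants with no diary for that vaccination. It can understate AE rates, including immediate AEs. The wording is firmer for Substudy A than for Substudy B. The size is unknown and probably small. The ceilings of about 2-12 of 125 and 2-10 of 100 per group rest wholly on the assumed 2-10% non-transmission.

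Three stronger readings are tempting and do not hold:

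- That these participants' reactions are all counted nowhere. Serious events and those leading to discontinuation are explicitly kept.
- That reactogenicity rates are lowered. Participants without a diary leave both numerator and denominator; any bias depends on how their true rate compares with the rest, about which the documents give no data.
- That the 65% local-reaction rate in Protocol 10.10.11.5 converts the ceiling into an expected count. That rate is a planning assumption for the 1.0-mL formulation in Substudy B. It does not describe the placebo, qIRV-alone or RSVpreF-alone groups, and using it would require every reaction to have been entered on the CRF.

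The point is worth settling before database lock, because a stated rule can give a wrong count in a primary safety table.

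**What to change.** In SAP 3.1.3.3, including item 2, state that a CRF event is removed from the AE derivations only if it was actually pooled into the reactogenicity analysis for that participant and that vaccination. Any other flagged event stays in the AE derivations and is identified in a listing. Make the same change in 3.2.1.1, including item 2, and correct its cross-reference so that it names the Substudy B derivations.

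The cost is about one sentence in each section, one programming condition and one listing. There is a small downside: solicited-type events would then count as AEs only for participants without a diary, so AE rates would rise slightly with diary non-completion. A footnote to the AE tables giving the number of such events per group lets the reader allow for this.

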1.1.2. Substudy B

The formulation development of combination vaccines requires consideration of to determine whether the ultimate product achieves the desired effects in a safe and tolerable manner.

A prior study of healthy adults 18 to 40 years of age who received anterolateral thigh injection with 5 suspensions containing the same components as excipients of a combined pertussis—inactivated poliomyelitis—Haemophilus influenzae type b pediatric vaccine investigated the incidence of local pain and burning sensation.

This is a Phase 1b study in healthy participants ≥50 years of age. Substudy B will investigate 2 formulations of RSVpreF + qIRV of differing volumes and osmolarities. The first combination is a bedside mix of CCI

, yielding a final injection volume of 1.0 mL CCI

The second combination is a bedside mix of to yield a final injection volume of 0.5 mL. The 0.5-mL CCI combination would result in CCI with the

potential to influence reactogenicity at the injection site. These combinations will be evaluated for safety, tolerability, and immunogenicity, with the goal of selecting a formulation for further study.

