8.3. Safety Assessments

Substudy A planned time points for all safety assessments are provided in the SoA – Substudy A.

Substudy B planned time points for all safety assessments are provided in the Schedule of Activities – Substudy B.

Unscheduled safety measurements may be obtained at any time during the study to assess any perceived safety issues.

A clinical assessment and medical history will be performed on all participants at their first visit to establish a baseline. Significant medical history and observations from any physical examination, if performed, will be documented in the CRF.

AEs and SAEs are collected, recorded, and reported as defined in Section 8.4.

Acute reactions within the first 30 minutes after administration of each study intervention will be assessed and documented in the AE CRF.

Safety parameters also include reactogenicity e-diary reports of local reactions, systemic events (including fever), and use of antipyretic medication that occur in the 7 days after administration of the study intervention. These prospectively self-collected occurrences of local reactions and systemic events are graded as described in Table 1, Table 2, and Table 3.

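### Flagged nonserious reactions starting within 30 minutes are left out of the planned immediate-AE summary, so their 30-minute timing is reported nowhere

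*SAP*

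**What the plan says.** - **Collection.** Protocol 8.3: "Acute reactions within the first 30 minutes after administration of each study intervention will be assessed and documented in the AE CRF". The visit procedures (Protocol 10.9.10.6.1 and 10.10.10.6.1) have blinded staff observe each participant for at least 30 minutes and note the time of onset.
- **Pooling.** SAP 3.1.3 takes "any AEs reported within 7 days after vaccination that match with those flagged PTs" and merges them with the e-diary data, related or not, using the higher grade when both sources report the same reaction on one day. Clinical review settles the list of terms before database lock; the list is not in the SAP. CRF reactions are not used for reactogenicity when a participant has no e-diary data.
- **Exclusion.** For a CRF event classed as reactogenicity, SAP 3.1.3.3 states that "this AE record will not be included in any of the derivations included in Section 3.1.3.3 and Section 3.1.3.4". The only exemption is that "if those reactogenicity AEs lead to discontinuation or were serious AEs, they will still be included in AE data".
- **Immediate AEs.** Derivation 3 in that section is "Any immediate AE reported after vaccination (AE start time is within 30 minutes after vaccination". It covers events on the day of vaccination, and only those "with nonmissing AE start time that is within 30 minutes of vaccination, will be included".
- **Substudy B.** SAP 3.2.1.1 has its own derivation 3 in the same terms. It then invokes "The same algorithm as stated in Section 3.1.3, for any AE reported in the CRF that was considered as reactogenicity", but names 3.1.3.3 and 3.1.3.4, not 3.2.1.1, as the sections from which the record is dropped.
- **Reporting.** SAP 6.1.4.2 plans a supplementary summary of immediate AEs, and 6.1.6 carries the presentation over to Substudy B.

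**The concern.** The study collects a clock time for reactions seen in the first half hour, plans a table for exactly that window, and then filters out of it the reactions most likely to be seen there: injection-site pain, redness, swelling, headache, nausea. Serious and discontinuing reactions are exempted from the filter; immediate ones are not.

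The timing matters most in Substudy B. Its two formulations differ in volume and osmolality, and Protocol 1.1.2 says the 0.5-mL combination has "potential to influence reactogenicity at the injection site". The rationale cites an earlier study of local pain and burning in healthy adults, and the entry in the reference list that appears to match it is titled for burning felt at and just after the injection. If one formulation hurts more as it goes in, the staff-observed record is the only source that can separate this from soreness later the same day. A near-empty immediate-AE row could be read as showing that few such reactions occurred.

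**Working it through.** **1. Where each type of event goes.** The rules in SAP 3.1.3 and 3.1.3.3, applied to a CRF event with recorded onset within 30 minutes:

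| Event | Immediate-AE summary | 7-day reactogenicity | 30-minute timing shown |
|---|---|---|---|
| Term not flagged | Yes | No | Yes |
| Flagged; serious or led to discontinuation | Yes | Yes, if e-diary data exist | Yes |
| Flagged; neither; e-diary data exist | No | Yes, on Day 1 | No |
| Flagged; neither; no e-diary data | No | No | No |

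The third row loses timing only. The fourth row loses the event from both summaries.

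**2. Whether another table restores the timing.** SAP 3.1.3.1.4 defines onset by day. SAP 3.1.3.1.5 and 6.1.3.2 give presence on each of the 7 days, and 3.1.3.1.2 gives maximum severity. All are on a whole-day scale, so none separates the first 30 minutes from the rest of Day 1.

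**3. Substudy B wording.** Read literally, the exclusion in 3.2.1.1 reaches only 3.1.3.3 and 3.1.3.4, so derivation 3 of 3.2.1.1 would be untouched. Read by its reference to the same algorithm, it applies to 3.2.1.1 as well. The second reading is more likely intended, but two programmers could produce different tables. In both sections derivation 2 carries its own reactogenicity exclusion and derivation 3 does not.

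**4. The plan's own figure.** Protocol 10.10.11.5 gives 82% power for at least 1 local reaction, 65% versus 90%, 50 per group, Fisher exact test. Alpha is not stated there; two-sided 0.05 is assumed. Power = Σₓ Σᵧ Bin(x; 50, 0.65) · Bin(y; 50, 0.90) · 1[Fisher p ≤ 0.05] = 82.03%, so the figure reproduces. At the planned 100 per group the same contrast has 98.9%. The sized endpoint already counts immediate reactions on Day 1 for anyone with e-diary data, so neither value changes.

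**5. How far an immediate difference could be diluted (assumed rates).** The documents give no 30-minute rates. With 100 per group, two-sided Fisher power for a difference in 30-minute reactions is:
- 5% vs 15%: 58.6%
- 5% vs 20%: 88.3%
- 5% vs 25%: 98.1%

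Take the 10-point excess in the first line against the protocol's 65% background. It adds between 0 points to the 7-day any-local-reaction rate (all the extra reactors would have reported one anyway) and 10 points (none would). The chance of a significant 7-day difference then runs from 3.4% (65% vs 65%), through 8.9% (65% vs 70%), to 28.5% (65% vs 75%). The analysis is descriptive, so these figures only gauge sensitivity. A Day 1 comparison would sit closer to the 30-minute contrast, but the documents give no Day 1 rates.

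**6. What an emptied row would report.** With 0 of 100, the upper Clopper-Pearson limit is 1 − 0.025^(1/100) = 3.6%. That interval would describe only unflagged, serious or discontinuing events, although the row is labelled as all immediate AEs.

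**The case against.** The strongest reply is that nothing important is lost. Flagged events from participants with e-diary data move into 7-day local reactions and systemic events, which are primary Substudy B endpoints, at the higher grade of the two sources, and presence on Day 1 is summarised by formulation. No Substudy B objective or estimand concerns the first 30 minutes. Protocol 2.3.1 ties the observation period to anaphylaxis, which stays in the row unless its term is flagged. Protocol 8.3.4 keeps e-diary data out of the CRF adverse events so that reactions are not reported twice.

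Most of this stands. A reader might infer that the exclusion removes the injection-site signal from the Substudy B comparison; the documents do not support that, because the events are relocated and the onset times remain in the CRF. A reader might also infer that no immediate reaction can appear in the row. That is too strong as well: serious, discontinuing and unflagged events stay. Burning is not a prompted diary item, and with the list unseen its place is undetermined.

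Adding immediate AEs to the existing exemption would also be a poor remedy. That exemption returns records to the AE data generally, so solicited reactions would enter any-AE and severe-AE counts and clash with derivation 2.

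What the reply does not answer is that the planned immediate-AE table omits events that meet its own definition, that no other table shows them on that scale, and that participants without e-diary data drop out of both.

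**Conclusion.** The point holds as a limited reporting gap. For Substudy A the text is clear: flagged, nonserious, non-discontinuing reactions with onset within 30 minutes are missing from the immediate-AE summary. For Substudy B the same is probable but not certain, given the cross-reference. The loss is one of timing where e-diary data exist, and of the event itself where they do not.

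The number of events cannot be given, because the documents contain no 30-minute rates and no flagged-term list. The conclusion assumes that the list will include at least the solicited reactions, and that the exclusion applies to a flagged record even when there is no e-diary for it to be pooled with; the SAP does not say otherwise. The primary reactogenicity comparison for participants with e-diary data, the sample size and the 82% power are unaffected. It should be corrected because Substudy B is meant to select a formulation and its cited background concerns sensations at injection.

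**What to change.** - In SAP 3.1.3.3 and 3.2.1.1, state that the reactogenicity exclusion does not apply to derivation 3. Every CRF event with recorded onset within 30 minutes then counts in the immediate-AE summary by vaccine group, pooled or not. This also settles the burning question for that table.
- Leave the any-AE, related-AE and severe-AE derivations as they are for participants with e-diary data.
- Correct the exclusion in 3.2.1.1 so that it names that section.
- For participants with no e-diary data, keep CRF reactions in the AE summaries, including derivation 2, since nothing is pooled for them.

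The cost is a few sentences in the SAP, ideally before the flagged-term list is settled. No new data or change of sample size is needed. One event can appear in both the immediate-AE and reactogenicity tables, which a footnote handles. AE counts rise slightly for any participants who returned no e-diary data.
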